Due to increasing level of uremic toxins, perennial diet control, antibiotic application and oral iron, the symbiotic relationship between host and microorganism of the CKD patients is broken, which leads to intestinal flora imbalance and manifests as a significant decrease in anaerobic probiotics and a significant increase in aerobic harmful flora⁴. Intestinal flora could produce an excess of uremic toxins such as indoxyl sulfate (IS), p-cresyl sulfate(PCS), trimethylamine N-oxide(TMAO), acetanilide and lipopolysaccharide during the fermentation of proteins and amino acids. Physiologically, these enterogenous urotoxins are secreted through renal tubules and cleared by the kidneys, however, CKD patients have renal insufficiency, and these medium molecular toxins are difficult to be cleared by dialysis, resulting in the accumulation of toxins in the blood. A lot of clinical studies show that urotoxins not only promote the occurrence and development of CKD but also produce effect on anemia, malnutrition, bone-metabolism disorder, cardio- and cerebrovascular

complications. Because of increasing intestinal urotoxin, damage of intestinal mucosal epithelial barrier, delayed intestinal drainage, intestinal mucosa edema and ischemia, and the nutrient absorption of CKD patients are reduced. In addition, with a low protein diet, CKD patients are prone to malnutrition. Intestinal flora imbalance, translocation and accumulation of enterogenous urotoxin and malnutrition can form a vicious cycle, leading to poor prognosis of patients⁶. Current studies show that polyamine toxoid can inhibit EPO activity and affect erythropoiesis⁷. IS and PCS can induce osteodystrophy and disordered bone metabolism by several mechanism⁸, like promoting parathyroid hormone resistance, inhibiting osteoclast function and osteoblast differentiation. Besides, IS and PCS can accelerate renal fibrosis by inhibiting the expression of kidney protective genes (such as Klotho), activating renin-angiotensin-aldosterone system, mediating oxidative stress and activating inflammatory response⁹. The increasing plasma TMAO levels can lead to renal atherosclerosis¹⁰. IS, PCS and TMAO can damage vascular endothelial cells through various pathways, promote vascular calcification and atherosclerosis, and lead to cardio- and cerebrovascular events¹¹⁻¹². Therefore, preventing intestinal flora imbalance and reducing the production and accumulation of urotoxin can provide new therapeutic approaches for anemia, malnutrition, disordered bone metabolism and other complications in CKD and MHD patients.

Currently, there are several therapeutic approaches for intestinal flora imbalance, including ①High dietary fiber, low animal protein and low fat diet; ②Toxin adsorbents like activate carbon; ③Fecal transplantation; ④Micro ecological preparations like probiotics, prebiotics, synbiotics and postbiotics. CKD and MHD patients need to restrict potassium intake, which will inevitably lead to the reduction of fructose and cellulose, so that simply diet adjustment has little effect on the improvement of CKD. Activate carbon is considered to be an intestinal purifier which

can effectively reduce the absorption of gastrointestinal toxins in acute poisoning, but long-term application can cause gastrointestinal adverse reactions such as nausea and vomiting, which causes intestinal peristalsis dysfunction and even intestinal obstruction. Fecal transplantation is used to transfer of microbial flora extracted from the stool of healthy people into the intestines of patients, but it's still difficult to ensure the long-term stability and safety of the donor stool and find a suitable donor. According to current studies, using micro ecological preparations to increase probiotics can play a role in prevention and treatment of CKD.

Probiotics are a kind of active microorganisms which are beneficial to human body and can improve the structure of intestinal flora. Studies have confirmed that bifidobacterium preparations can effectively bind to human intestinal mucosal epithelial cells to build biological barriers after oral entry into the intestine. Bifidobacterium can produce extracellular glycosidase to degrade complex polysaccharides so that it inhibits pathogenic bacteria significantly¹³. Lactobacillus and bifidobacterium formulations have been shown to reduce PCS and IS levels in patients and reduce systemic inflammatory responses¹⁴. Moreover, bifidobacterium can promote intestinal peristalsis and drainage of intestinal toxic metabolite. Prebiotics are organic substances that are not digested and absorbed by the host but can promote the proliferation and metabolism of beneficial bacteria in the body. The intestinal bifidobacterium can increase significantly when dietary adjustment is combined with the intake of prebiotics (such as inulin)¹⁵. Symbiotic is a combination of probiotics and prebiotics and it can both supplement probiotics and promote the growth and survival of probiotics¹⁶. Therefore, the application of micro ecological preparation, supplementing probiotics, prebiotics and symbiotics can stimulate and regulate intestinal flora, alleviate CKD disease to a certain extent, and improve the quality of life of patients, which is of great significance. There are several

disadvantages of living bacteria components such as high requirement for preservation and transportation, potential safety risks, intolerance to stomach acid, and non-use with antibiotics. In contrast, inactivated probiotics have their unique advantages. Recently, inactivated probiotics preparations attract more and more attention and are known as probiotics. Probiotics are those bioactive compounds produced by probiotics when they consume prebiotics, including short-chain fatty acid, lipolyaccharide, enzyme, exopolysaccharide, cell-free supernatant, inactivated probiotic bacteria or cell fragments (e.g. cell wall fragments, bacterial lysates, etc.) and other metabolites (e.g. vitamins, amino acids, etc.). Short-chain fatty acids in postbiotic are an important energy source for cells and play a vital role in the renewal of cells in the intestinal wall. They help to maintain the integrity of the intestinal barrier and can be used as an adjunct therapy of inflammatory bowel disease and other digestive disorders. Postbiotics can regulate microbiota directly and indirectly and inhibit growth of pathogenic microorganism, for example, bacteriocin secreted by lactic acid bacteria can inhibit the growth of intestinal pathogens.

MHD patients have a high incidence of intestinal flora disorders. Malnutrition and other complication progression causing by intestinal flora disorders in MHD patients currently lacks perfect treatment options, affecting their life quality and prognosis, increasing the hospitalization rate and medical costs. In elderly patients, malnutrition, intestinal dysfunction, and reduced quality of life are more prominent. The purpose of the study is to investigate the effects of exogenous supplementation of intestinal probiotic metabolites on life quality, nutrition, intestinal flora and urotoxins in elderly MHD patients, and to explore the feasibility and effect of new treatment methods.

2. Purpose

The purpose of the trial is to explore the effect of exogenous postbiotics supply on the quality of life and nutritional status of elderly hemodialysis patients.

3. Method

3.1 Design

The study is a multicenter prospective open labeled randomized controlled trial. Elderly patients with age ≥ 65 years and received hemodialysis treatment for more than 6 months will be included in the study. After enrollment, the patients will be educated about how to keep diet records and then they will be randomly divided into group A and group B in a 1:1 ratio. The patients in group A will receive oral postbiotics and group B receive placebo. The treatment period is 12 weeks. Subsequently, group A ends the trial, and group B enters the remedial treatment period, receiving oral postbiotics, and the treatment cycle is 12 weeks. At 0, 12th and 24th week, quality of life score, nutrition evaluation, diet status and gastrointestinal symptom score of patients will be evaluated. The stool and serum of patients will be collected for intestinal flora and urotoxins IS, PCS and TMAO measurements. The improvement of biochemical indicators will be evaluated. The biochemical indicators include blood creatinine, urea nitrogen, albumin, prealbumin, hemoglobin, blood calcium, blood phosphorus, whole parathyroid hormone, blood potassium, C-reactive protein, ferritin, transferrin saturation, et al. During the whole intervention process, patients will be encouraged to maintain intake of protein and fiber and keep a diet log.

During the intervention process, the process of hemodialysis and other diagnosis and treatment behaviors will be performed according to clinical routine.

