3.3.3.2 Introduction Period (-2nd to 0 week before the randomization)

The second follow-up visit should be on the first hemodialysis day of the week (e.g. Monday or Tuesday). The following list summarizes the procedures for the introduction period:

- We should record the most recent URR and spKt/V of patients within last 1 month prior to the randomization.
- We should record any change of medications after the last follow-up visit.
- We should record the diet of patients.
- We should score the rating scales listed in the flowchart above.
- We should perform the anthropometric measurements listed in the flowchart above.
- We should collect the results of recent routine blood test before dialysis of the patient.
- We should collect the blood and stool samples for urotoxins and intestinal flora baseline measurements.
- The patients will be divided randomly into treatment group and control group. Patients in the treatment group will be given oral intestinal flora metabolites 3 times a day and 1 bag each time. Patients in the control group will be given placebo.
- The therapeutic medications should be supplied.

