3.4 Outcomes

3.4.1 Primary Outcome Measure:

Outcome Measure	Measure Description	Time Frame
Changes of nutritional status from the baseline to the end of treatment and differences between the intervention group and the placebo group.	Nutritional status of the patient is defined as the results of physical examination and SGA-7 rating scale.	From the baseline to the end of treatment.
Changes of quality of life from the baseline to the end of treatment and differences between the intervention group and the placebo group.	Quality of life of the patient is defined as the scores of gastrointestinal symptom rating scale (GSRS), kidney disease life quality scale (TM-SF36) and enervation frailty scale (EFS).	From the baseline to the end of treatment.

3.4.2 Secondary Outcomes:

Outcome Measure	Measure Description	Time Frame
Changes of enterogenous urotoxin level from baseline to the end of treatment and difference between the intervention and placebo group.	Enterogenous urotoxin level is defined as the serum level of IS, PCS and TMAO. The levels of serum IS, PCS and TMAO will be measured by mass spectrometry.	From the baseline to the end of treatment.

Changes of intestinal flora structure from the baseline to the end of treatment, and the difference between the intervention group and the placebo group.
	
The structure of intestinal flora will be measured by the V3-V4 region of 16S rDNA with MiSeq PE300 sequencing platform for high-throughput analysis and described by number of the flora.
	
From the baseline to the end of treatment.

Changes of routine biochemical indicators from the baseline to the end of treatment, and differences between the intervention group and the placebo group.
	
The routine biochemical indicators include serum creatinine, urea nitrogen, albumin, prealbumin, hemoglobin, serum calcium, blood phosphorus, total parathyroid hormone, serum potassium, carbon dioxide, C-reactive protein, ferritin, transferrin saturation.
	
From the baseline to the end of treatment.

Changes of dietary intake from the baseline to the end of treatment, and the difference between the intervention group and the placebo group.
	
Dietary intakes of the patients will be described by the diet record.
	
From the baseline to the end of treatment.

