3.5 Exposure

Metabolites of intestinal probiotics are those bioactive compounds produced by intestinal bacteria when they consume prebiotics, including short-chain fatty acid, lipolyaccharide, enzyme, exopolysaccharide, cell-free supernatant, inactivated probiotic bacteria or cell fragments (e.g. cell wall fragments, bacterial lysates, et al) and other metabolites (e.g. vitamins, amino acids, et al). Supplying exogenous

intestinal probiotic metabolites is one of the therapies for intestinal flora disorder. It can regulate intestinal flora, improve nutritional status, reduce serum levels of urotoxins and improve quality of life. Patients usually need 8-12 weeks to take the postbiotic product. Here is the introduction of postbiotic product.

The **Postbiotics** used in this study is Yi'en Yuan Honey Fermented Drink, which is made from water, edible brown sugar, and honey as raw materials. It is fermented by a mixture of plant lactic acid bacteria and coagulating Bacillus, and then inactivated at high temperature. The production of the product follows the GB7101 standard, and no live bacteria or related prohibited ingredients are detected in the finished product, which meets the food and beverage standards. According to *NJ-W22070721 Yi'en Yuan Honey Fermented Drink* and *SH-W23040315 Honey enzyme beverage test report*, the product includes carbohydrate 4.0-4.7g/100mL, potassium about 60.9mg/100mL, phosphorus about 2.8mg/mL. According to the concentration shown above, if you consume 150ml of the product a day, you will intake carbohydrate 6.0-9.1g, potassium 90mg, phosphorus 4.2mg, which is far lower than the daily intake of these substances from the diet and can be used for dialysis and diabetic patients. Since its launch in June 2021, no side effects have been reported.

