3.6 Sample Size

The study is a randomized control trial. There is no previous related published study so that it's an exploratory trial. According to the study of other micro ecological preparations, the sample size of each group should be 20. Taking into consideration the dropout rate of 20% by the end of the study, a sample size of 30 per group is planned for this study.

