4.2 Subject Risk

During the trial, the treatment group will take 150ml of Yi En Yuan honey yeast drink each day. The product is made of water, edible brown sugar and honey. It's mixed fermented by plant lactic acid bacteria and Bacillus coagulates and sterilized at a high temperature. The product is produced according to GB7101 standard, and there is no live bacteria and prohibited ingredients in the product, which meets the food and beverage standards. According to *NJ-W22070721 Yi En Yuan honey yeast drink* and *SH-W23040315 Honey enzyme beverage test report*, the product includes carbohydrate 4.0-4.7g/100mL, potassium about 60.9mg/100mL, phosphorus about 2.8mg/mL. According to the concentration shown above, if you consume 150ml of the product a day, you will intake carbohydrate 6.0-9.1g, potassium 90mg, phosphorus 4.2mg, which is far lower than the daily intake of these substances from the diet and can be used for dialysis and diabetic patients. Since its launch in June 2021, no side effects have been reported. Patients in the control group will be given 150ml of placebo each day which is made of water and food coloring.

Blood samples of the subjects are taken at the same time as routine clinical tests without additional samples. The risks are the same as those in daily blood drawing tests, including puncture pain, the need for a second puncture when the blood drawing is not successful, and a small amount of subcutaneous bleeding caused by poor compression after blood drawing. Blood drawing will be performed by experienced nurses. The venous blood collection routine will be strictly followed, and after blood

collection we will press effectively to stop bleeding. If the puncture is unsuccessful, we will stop the second puncture and we will try again after 24 hours.

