5.1 Quality Control of Clinical Research Process

Clinical data collection will be performed by the clinicians. The clinicians participating in this study must have received relevant training and understand

thoroughly about the objectives and procedures of the research. Besides, they should be able to collect high-quality clinical data and biological samples and then pass them to the data analysts and laboratory testers after preliminary collation and store. In the process, they should ensure the rights and interests of the subjects. Each subject will be numbered individually by the clinicians in order to protect their privacy and conduct blind analysis. The data of each subject will be verified by two clinicians to ensure authenticity and reliability.

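### Section 3.1 calls the trial open label yet gives controls a placebo, and nothing masks patients, questionnaire staff or raters, so the subjective primary scales are open to expectation and rating bias

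*Protocol*

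**What the plan says.** Section 3.1 states: "The study is a multicenter prospective open labeled randomized controlled trial". The same paragraph continues: "The patients in group A will receive oral postbiotics and group B receive placebo". The placebo recurs in the flowchart, in section 3.3.3.2 ("Patients in the control group will be given placebo"), in the outcome definitions of section 3.4 and in section 4.2.

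The two drinks are described differently. Section 3.5 describes the active product as a fermented drink "which is made from water, edible brown sugar, and honey as raw materials". Section 4.2 says: "Patients in the control group will be given 150ml of placebo each day which is made of water and food coloring". The protocol does not say that taste, appearance or packaging is matched.

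The only reference to blindness is in section 5.1: "Each subject will be numbered individually by the clinicians in order to protect their privacy and conduct blind analysis". Section 5.4 adds standard procedures and training for the scales.

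Section 3.4.1 has two primary outcomes. Nutritional status is physical examination plus SGA-7. Quality of life is GSRS, TM-SF36 and EFS. Section 3.2 has trained staff complete the questionnaire, while section 3.7 has patients complete the kidney disease scale themselves.

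**The concern.** A placebo serves mainly to hide the allocation, and an open label gives that up. The protocol states both and does not say which governs. Who is masked is part of the design that section 3.1 itself fixes, so this is not a detail left to an analysis plan.

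If open label governs, a patient who knows that he or she is on the product may report fewer symptoms or better function. Staff who know the arm may record or score more favourably. A week-12 difference on the subjective scales could then not be separated from expectation. Control patients would drink a placebo daily for 12 weeks while the trial loses most of the protection that a placebo should give.

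The timing of randomisation bears on the same issue. If the arm is known before the baseline scales are scored, the baseline is exposed too.

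**Working it through.** **1. Is anyone masked?** Section 5.1 speaks of numbering subjects for privacy and analysis, and the numbers are assigned by the clinicians who collect the data. At most this masks analysts or laboratory testers. Section 5.4 concerns consistent scale administration, which reduces rater variability but does not hide the arm. No other section addresses masking.

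**2. Which primary measures are exposed?**
- TM-SF36: 36 items, completed by the patient (section 3.7, Appendix B). Exposed.
- GSRS: 16 symptom-severity items (Appendix C). Exposed through the patient and, if staff complete it as section 3.2 suggests, also through the interviewer.
- SGA-7 total: the components have anchors, but the total is an overall judgement from 1 to 7 and not an average (Appendix A). Exposed through the rater.
- EFS, 17 points (Appendix D): performance items are the clock test 2 + timed walk 2 = 4. Factual items are hospitalisations in the past year 2 + five or more pills 1 = 3. The other patient-answered items are overall health 2 + help needed 2 + social support 2 + forgetting medicine 1 + weight loss 1 + low mood 1 + urinary control 1 = 10. Check: 4 + 3 + 10 = 17. The exposure lies mainly in these 10 points.
- Physical measurements and the laboratory secondary outcomes: much less exposed.

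**3. When does randomisation happen?** The last bullet of section 3.3.3.1 randomises eligible patients after screening. The headings of sections 3.3.3.1 and 3.3.3.2 both date their periods before randomisation, and the list in 3.3.3.2 puts randomisation after the scales, measurements and samples. Section 3.2 dates the first questionnaires and measurements to the study's opening week, which does not settle whether they come before or after allocation.

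**4. Illustration of size.** The plan has no figure to reproduce here. The inputs are 30 per arm and 20% dropout (section 3.6), so 30 × 0.8 = 24 completers; 20 per arm, also from section 3.6; and the 0.05 level and independent t test from section 3.8, with a two-sided test assumed. The bias *b*, in SD of the change score, is an assumption.

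With no true effect, the rejection probability comes from a noncentral t with 2n − 2 degrees of freedom and noncentrality b / √(2/n). For n = 24, √(2/24) = 0.289, so b = 0.2, 0.3 and 0.5 give noncentralities of 0.69, 1.04 and 1.73.

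| Assumed net bias | n = 24 per arm | n = 20 per arm |
|---|---|---|
| 0.2 SD | 10.4% | 9.5% |
| 0.3 SD | 17.5% | 15.2% |
| 0.5 SD | 39.6% | 33.8% |

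Simulation with 100,000 runs per cell agrees (10.5%, 17.6%, 39.5%; 9.6%, 15.2%, 33.6%). A normal approximation at n = 24 gives 10.7%, 18.0% and 41.0%.

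The smallest observed difference that reaches P<0.05 is t(0.975, 2n − 2) × √(2/n), which is 0.58 SD for n = 24 and 0.64 SD for n = 20.

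**The case against.** Open label is a permissible design, and section 3.6 says: "There is no previous related published study so that it's an exploratory trial". On this view the fault is one unreconciled word, and masking the supply is a redesign. The first half stands, and it limits the point to how the scales can be interpreted. It does not remove the problem: the stated purpose is the effect on quality of life and nutrition, section 3.8 applies P<0.05, and the placebo is already being supplied.

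The illustration would hold for any trial of this size and says nothing about how likely such a bias is here. That stands too, so the severity rests on the text and not on those percentages.

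A reader might infer three stronger things that the protocol does not support.
- **That every patient-answered EFS point is exposed.** Hospitalisations and pill count are factual and checkable, and at week 12 most of the 12-month hospitalisation window predates treatment.
- **That masking with the present placebo would fail.** Coloured water may be distinguishable from a fermented honey drink, but in weeks 0 to 12 each patient takes only one of them, and recognition depends on what patients are told. The consent form is not available to this review. It is a risk, not an established failure.
- **That randomisation definitely precedes baseline.** The bullet in 3.3.3.1 can be read as announcing the next step. The sections conflict and need aligning; they do not prove early allocation.

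**Conclusion.** The contradiction between an open label and a placebo control is certain from the text, as is the absence of any masking of patients, questionnaire staff or raters. Run as written, GSRS, TM-SF36, the SGA-7 total and the subjective EFS items carry an avoidable risk of expectation and rating bias. The remaining primary and secondary measures are much less affected.

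The size is unknown. The range of about 10% to 40% for the per-scale false-positive rate rests on an assumed net bias of 0.2 to 0.5 SD, 24 per arm, a two-sided t test and no true effect. A reader might conclude that the trial is invalid, or that a positive result would be spurious. Neither follows: the trial is labelled exploratory, and the bias is possible, not demonstrated. The point should be fixed because part of the remedy is cheap and protects the primary outcomes.

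**What to change.** 1. **Preferred: mask weeks 0 to 12.** Replace the open-label wording in section 3.1 and state who is masked. Dispense product and placebo in identically packaged coded bags. Keep the code from patients, from the staff who complete questionnaires (section 3.2) and from SGA-7 and EFS scorers, and open it for a patient only after the week-12 scores and samples are complete. Acknowledge in section 4.2 that the two drinks may be distinguishable, and match them where practicable.
2. **If open label is kept**, say so without ambiguity. Where existing trained staff who do not know the arm are available, have them score SGA-7 and EFS and administer the questionnaires. State that differences on the subjective scales are open to expectation bias.
3. **In either case**, delete the randomisation bullet in section 3.3.3.1 and align the baseline timing in section 3.2, so that all baseline scores and samples precede randomisation and the first supply at Follow-up 2.

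Cost: wording changes in sections 3.1, 3.2, 3.3.3.1 and 4.2; for option 1, supply coding and someone who does not score to hold the code. The protocol does not show whether such staff exist at each site. A closer-matched placebo may need reformulation, which is not clearly cheap. No visits or measurements are added. Group B is unmasked after week 12 in any case, but by then the randomised comparison has ended.
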